#### **6.4 Study Specific Tolerance for Inclusion/Exclusion Criteria**

Subjects who fail to meet one or more of the inclusion criteria or who meet any of the exclusion criteria will not be enrolled in this study. Waivers of any of the above study entry criteria will not be granted.

#### **6.5 Screen Fail Criteria**

Any consented patient who is excluded from the study before randomization is considered a screen failure. All screen failures must be documented with the reason for the screen failure adequately stated. If a subject screen fails prior to randomization, they can be rescreened once if the site staff feels they meet eligibility criteria and following confirmation from the Sponsor-Investigator or designee. Rescreened subjects are required to complete all screening procedures (i.e., test results from previous screenings cannot be used).

### **7 CONCURRENT MEDICATIONS**

All subjects should be maintained on the same medications throughout the entire study period, as medically feasible, with no introduction of new chronic therapies.

## 7.1 Allowed Medications and Treatments

For both the randomized and open-label periods, standard therapy for CF is allowed except for treatments noted in the conditionally allowed and prohibited medications sections below.

Ongoing chronic treatment (>30 days prior to Visit 1) with inhaled dornase alpha, hypertonic saline, short and long acting bronchodilators, FDA-approved CFTR modulators, high dose ibuprofen, low-dose inhaled or systemic steroids and airway clearance is allowed.

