## 2.1 Risk / Benefit Assessment

No experimental or new medications are being introduced to subjects during this study. Removal of chronic azithromycin may decrease lung function or increase the rate of pulmonary exacerbation, based on prior studies of azithromycin in similar patients. Our preliminary data does not support this concern and suggest that removing azithromycin may be protective in the majority of subjects also using inhaled tobramycin. This includes better clinical outcomes in lung function (FEV1), patient reported quality of life, and time to need additional antibiotics. However, a withdrawal study of either medication has never been reported and our preliminary data on lung function may not fully predict the risk of pulmonary exacerbation. Subjects experiencing a pulmonary exacerbation will be treated but will not be removed from the study.

Identifying an undesirable drug-drug interaction pertinent to over 50% of US patients with CF has clear and important safety and efficacy implications. Given that both of these medications benefit from strong support in US consensus guidelines, answering this question is a high priority.

Recent reports raise concern about potential proarrhythmic cardiotoxicity with oral azithromycin treatment in non-CF populations. Patients with CF account for a significant portion of chronic azithromycin use in the US and cardiac arrhythmias have not been linked to this therapy. Similarly, the relative risk of cardiovascular death attributable to azithromycin was reported as <1 per 100,000 antibiotic courses in low risk patients. There are approximately 30,000 CF patients in the entire US, and a repeat study found no increased risk in younger, lower risk adult populations. However, this study provides an opportunity to analyze electrocardiograms (ECGs), focusing on any effect on QTc interval, in a group of CF subjects both on and off of azithromycin.

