## 4 STUDY DESIGN

### 4.1 Study Overview

This is a prospective, randomized, placebo-controlled, double-blinded study of azithromycin in subjects with chronic *Pa* airway infection using inhaled tobramycin. Subjects who have received two (2) or more cycles of inhaled tobramycin within the 24 weeks prior to enrollment will be recruited into the study. This study will investigate whether azithromycin is associated with poorer clinical and microbiologic outcomes as compared to placebo during concurrent administration of inhaled tobramycin.

[figure not shown]
Approximately 120 eligible subjects will be enrolled and randomized to either azithromycin or placebo at Visit 1, approximately 14 days prior to the start day of their next planned 28-day nebulized solution or dry powder tobramycin (TISP) cycle. Both tobramycin inhalation solution (TIS) and tobramycin inhalation powder (TIP) will be allowed, based on clinical prescription. Tobramycin solution should be nebulized with an approved nebulizer and air compressor.

Subjects will be randomized in a 1:1 fashion to azithromycin (500 mg three times per week) or matched placebo. Randomization will be stratified by FEV1 % predicted (25%-50%, >50%-75%, >75%), chronic oral azithromycin use for the past 30 days, inhaled tobramycin formulation (TIS or TIP), and site. Between Visit 1 (Day -14) and Visit 2 (Day 0), a two-week run-in period will be used to begin administration of either azithromycin or placebo. Among those randomized to azithromycin, the 2-week run-in period will be used to initiate azithromycin and standardize uptake prior to the start of the next TISP cycle. Among those randomized to placebo, the run-in period will be used as a standardized washout prior to the start of the next TISP cycle. Subjects will begin TISP at Visit 2 in addition to their continued dosing of randomized study drug treatment (azithromycin or placebo). Subjects will continue both TISP and study drug dosing for 28 days (up until Visit 3), which corresponds with the end of a clinically prescribed 4-week cycle of TISP.

Subjects completing the study through Visit 3 will be offered participation and consent to an 8-week open-label extension period during which azithromycin will be provided. During the open-label period, subjects will be instructed to remain off of TISP for the first 4-week period, followed by a 4-week period of TISP.

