### 6.2 Inclusion Criteria

#### Inclusion Criteria for Randomized Period:

1. Male or female  $\geq 12$  years of age at Visit 1
2. Documentation of a CF diagnosis as evidenced by one or more clinical features consistent with the CF phenotype and one or more of the following criteria:
  - Sweat chloride equal to or greater than 60 mEq/L by quantitative pilocarpine iontophoresis test (QPIT)
  - Two mutations in the CFTR gene believed to be disease causing in the opinion of the site investigator
  - Abnormal nasal potential difference (change in NPD in response to a low chloride solution and isoproterenol of less polarizing than -7 mV)
3. Written informed consent (and assent when applicable) obtained from subject or subject's legal representative
4. Two or more respiratory cultures (sputum, OP swab, BAL sample) growing *Pa* collected within the 12 months prior to randomization, at least 1 month apart, with at least one collected in the 6 months prior to randomization
5. FEV1% predicted between 25-100% at Visit 1

6. Off TISP and other inhaled anti-pseudomonal antibiotics for at least two weeks at randomization
7. Willingness to begin the next course of TISP at the scheduled Visit 2
8. Use of at least 2 cycles of TISP within 24 weeks prior to Visit 1
9. Ability to swallow capsules (similar in size to pancreatic enzyme capsules)
10. Most recent LFTs less than 4x ULN. Must be obtained within 12 months prior to Visit 1
11. Current azithromycin use at Visit 1 or prior chronic azithromycin use defined as four or more consecutive weeks. Subjects do not have to be using chronic oral azithromycin at Visit 1
12. Stable clinical status with no significant change in medication or airway clearance routine for four weeks prior to Visit 1, as determined by site investigator

Inclusion Criteria for Open-Label Period:

1. Completion of the randomized, placebo-controlled period (up through Visit 3)
2. Written informed consent (and assent when applicable) obtained from subject or subject's legal representative
3. Ability for subject to comply with the requirements of the study
4. Willingness to begin the next course of TISP at the scheduled Visit 4
5. Clinically stable at Visit 3 as assessed by the site investigator

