## 7.2 Conditionally Allowed Medications and Treatments

Acute treatment with drugs categorized as known to prolong QT interval is allowed according to the following:

- For drugs commonly used to treat CF patients (e.g. ciprofloxacin, levofloxacin, moxifloxacin, fluconazole, propofol, sevoflurane, ondansetron), study drug (azithromycin or placebo) or open-label azithromycin **does not** need to be stopped.
- For all other drugs categorized as known to prolong QT interval, acute use is allowed but study drug (azithromycin or placebo) or open-label azithromycin **must** be temporarily stopped during use of these medications. After acute treatment is completed, subjects should re-start study drug or open-label azithromycin on the next scheduled treatment day.
- Ongoing chronic treatment (>30 days prior to Visit 1) with antidepressant medications citalopram and escitalopram is allowed without affecting study participation if:
  - The subject has been using both chronic oral azithromycin AND citalopram (or escitalopram) consistently for greater than 30 days at Visit 1 AND
  - The Visit 1 ECG demonstrates QTc within the normal limits as defined by the protocol

Drugs known to prolong QT interval are described as follows: “Substantial evidence supports the conclusion that these drugs prolong the QT interval AND are clearly associated with a risk of torsades de pointes (TdP), even when taken as directed in official labeling”, and listed on the CredibleMeds® Website ([Composite List of All QT Drugs](#) under the category “Known Risk of TdP”).

Acute use of macrolide antibiotics may be required for certain infections and is allowed but also requires temporarily stopping the study drug or open-label azithromycin. The study drug or open-label azithromycin should be restarted on the next scheduled day following completion of the prescribed macrolide antibiotic.

Treatment for pulmonary exacerbations as required for acute care is allowed except for treatments noted in the prohibited medications section below. Physicians are encouraged to prescribe acute antibiotic therapy and initiate or increase the dose of acute systemic corticosteroids (defined as less than 10 days) only in the presence of increased symptoms suggesting a pulmonary exacerbation.

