### 7.3 Prohibited Medications and Treatments

For both the randomized and open-label periods, the following medications are prohibited (for the randomized period, between Visit 1 through Visit 3; for the open-label period, between Visit 3 and Visit 5).

- Investigational therapies
- Chronic inhaled antibiotics other than cycled TISP (e.g., Cayston®, colistin). Chronic treatment is defined as inhaled antibiotics prescribed as a maintenance therapy and not used temporarily to treat a pulmonary exacerbation.
- Increase in chronic systemic corticosteroid dose beyond prednisone equivalent of 10 mg per day, or initiation of chronic systemic (oral or intravenous) corticosteroids at any dose. Chronic use is defined as greater than 10 days continuous use.
- New or increase in ibuprofen dose of greater than 800 mg total dose per 24 hours for more than 5 days
- Nelfinavir, warfarin, haloperidol, or methadone

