## 10 EVALUATIONS BY VISIT

### Randomized Period

#### 10.1 Visit 1 – Day -14

\*A respiratory culture may be obtained prior to randomization to confirm eligibility criteria #4. If a respiratory culture is needed, the remaining Visit 1 procedures should be completed after confirming positive *Pa* culture results.

1. Review the study with the subject (subject's legal representative) and obtain written informed consent and HIPAA authorization and assent, if appropriate.
2. Assign the subject a unique study number.
3. If there is not a recent respiratory culture available, obtain culture to confirm eligibility:
  - Review culture results.
  - If *Pa* positive and meets criteria #4, schedule subsequent visit to complete remaining Visit 1 procedures.
  - If *Pa* negative, record as Screen Fail.
4. Review and record previous use of azithromycin and inhaled tobramycin.
5. Record demographics and CFF Registry ID, if consent obtained.
6. Record medical history, including a history of CF diagnosis and date.
7. Record concomitant medications.
8. Administer PRO questionnaires (CFRSD-CRISS and CFQ-R).
9. Perform a complete physical examination.
10. Measure and record height and weight.
11. Obtain and record vital signs.

12. Perform and record spirometry.
13. Collect blood or urine for pregnancy test (if female of child-bearing potential).
14. Obtain resting ECG.
15. If able to expectorate sputum, collect expectorated sputum.
16. Confirm subject eligibility.
17. Randomize to study drug.
18. Dispense study drug.
19. Review study drug dose and schedule with subject.
20. Provide subject diary and instructions for completion.
21. Remind subject to NOT use inhaled tobramycin between this day and Visit 2.
22. Instruct subject to bring study drug bottle, any remaining capsules, and diary to Visit 2.
23. Schedule subject for Visit 2.

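### The placebo washout of chronic azithromycin is clearly intended, but section 7.3 and the Visit 1 steps do not state it, and the per-protocol set would keep a dose-compliant placebo participant who continued a home supply

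*Protocol*

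**What the plan says.** **Intent.** Inclusion criterion 11 (protocol 6.2) admits participants with "Current azithromycin use at Visit 1 or prior chronic azithromycin use defined as four or more consecutive weeks". Section 4.1 then states: "Among those randomized to placebo, the run-in period will be used as a standardized washout" before the next tobramycin cycle. The synopsis and SAP 1.1 say the same. Section 2.1 treats withdrawal as a recognized risk: "Removal of chronic azithromycin may decrease lung function or increase the rate of pulmonary exacerbation".

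**Medication rules.** Section 7.1 and the synopsis set the default: "standard therapy for CF is allowed except for treatments noted in the conditionally allowed and prohibited medications sections below". A second paragraph in 7.1 lists chronic treatments that may continue, and azithromycin is not among them. Section 7.2 deals with short courses: "Acute use of macrolide antibiotics may be required for certain infections and is allowed but also requires temporarily stopping the study drug". The only place in section 7 that refers to a participant's own chronic azithromycin is the citalopram condition in 7.2 ("The subject has been using both chronic oral azithromycin AND citalopram (or escitalopram) consistently for greater than 30 days at Visit 1"), which does not say to stop it. In 7.3 the one antibiotic entry begins "Chronic inhaled antibiotics other than cycled TISP (e.g., Cayston®, colistin". The other entries cover investigational therapies, steroids, ibuprofen and four named drugs, none of them a macrolide.

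**Visit steps.** Section 10.1 records previous azithromycin use. Its only hold instruction is "Remind subject to NOT use inhaled tobramycin between this day and Visit 2". Appendix 1 likewise has a hold row for tobramycin alone.

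**Analysis sets.** The primary analysis uses all randomized participants with at least one dose. It is repeated in a per-protocol set, defined in 15.1, SAP 2.4 and SAP A.3 by two conditions: at least 80% of study-drug doses, and no need for acute antibiotics or steroids.

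**The concern.** Exposure to azithromycin is the randomized contrast. A current user assigned to placebo who keeps taking a home prescription is exposed to the drug the placebo arm is meant to lack. That pulls the estimated difference toward zero and could hide the antagonism the trial is looking for. A current user assigned to azithromycin who does the same takes the drug from two sources, in a trial that monitors QTc.

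A per-protocol analysis is where a reader would look to see whether such departures matter. Here the definition screens for missed capsules and acute treatments but not for non-study use of the randomized drug. If the m-ITT and per-protocol results agreed, that would give no reassurance about this form of contamination.

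**Working it through.** **Step 1. Follow one participant through the rules.** Take a chronic azithromycin user at Visit 1, randomized to placebo, who takes all 18 capsules, continues home azithromycin and has no exacerbation.

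| Rule | Effect on this participant |
|---|---|
| 7.1, default | Standard CF therapy is allowed unless noted in 7.2 or 7.3 |
| 7.1, list of continuing treatments | Azithromycin absent, so continuation is not endorsed. The list is not exhaustive, however: pancreatic enzymes are also absent, although 8.5.3 expects some participants to take them |
| 7.2, macrolides | Written for acute courses with study drug paused; chronic use is not addressed |
| 7.3 | Not named |
| 10.1 and Appendix 1 | Prior use recorded; hold instruction for tobramycin only |
| 8.6.2 | Study drug should be paused for someone prescribed a macrolide; the home drug is not stopped |
| Section 13 | Use of a conditionally allowed drug outside its conditions is a violation, so one could be logged |
| Per-protocol, doses | 18/18 = 100%, above 80%: kept |
| Per-protocol, acute antibiotics or steroids | None: kept |

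The per-protocol definition does not refer to section 13, so a logged violation would not remove the participant. If 8.6.2 were applied literally and the capsules paused for long enough, the count would fall below 0.80 × 18 = 14.4 doses. The participant would then leave the set, but because placebo was missed, not because azithromycin was taken.

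**Step 2. Reproduce the planned power.** Inputs from 15.6: 55 per arm, two-sided 0.05 t-test. The standard error is SD × √(2/55), which for SD 13 is 2.479. The noncentrality is 7.5/2.479 = 3.025 on 108 degrees of freedom, with critical value 1.982. Power is 0.850, against a stated 85%. For 8.65% and SD 13 it is 0.933, against a stated 93%. For 6.3% and SD 11 it is 0.845, against a stated 85%. All three agree.

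**Step 3. Illustrate dilution.** Let k of the 55 placebo participants continue and show the full azithromycin-arm change. The expected difference becomes effect × (1 − k/55). For k = 4 and 7.5%: 7.5 × 51/55 = 6.955; 6.955/2.479 = 2.805; power 0.794. The value of k is an assumption, as no document gives one.

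| Effect / SD | k = 0 | k = 4 (7.3%) | k = 8 (14.5%) | First k with power below 80% |
|---|---|---|---|---|
| 7.5% / 13 | 0.850 | 0.794 | 0.727 | 4 |
| 6.3% / 11 | 0.845 | 0.788 | 0.720 | 4 |
| 8.65% / 13 | 0.933 | 0.894 | 0.840 | 11 |
| 7.5% / 11 | 0.943 | 0.908 | 0.857 | 12 |

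If continuers lose only half the effect, k = 4 acts like k = 2. Power is then 0.824 at 7.5%/13, 0.915 at 8.65%/13 and 0.927 at 7.5%/11. Adding the extra variance from a mixed placebo arm changes little: at k = 4 and 7.5%/13, power is 0.790 instead of 0.794.

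**The case against.** The strongest reply is that the protocol already makes little sense unless home azithromycin stops. The washout is stated repeatedly. The open-label objectives contrast participants remaining on azithromycin with those switching to it. Section 7.1 leaves azithromycin out of the chronic treatments that may continue, 7.2 permits macrolides only for acute use with study drug paused, 8.6.2 pauses study drug for any prescribed macrolide, and section 13 can make use outside those conditions a violation. Current use is a stratification factor, and medications are reviewed at every visit and changes entered in the diary, so continued use should be visible.

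Most of this stands. A reader might infer that the plan leaves the washout wholly unenforced, or that sections 7 and 7.4, by asking for stable medication, tell placebo participants to stay on azithromycin. The documents support neither reading. Sections 7 and 7.4 are best taken as covering background therapy, and the provisions above point toward stopping. The Study Manual and consent form, which are not among the documents, may also carry the instruction.

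The reply does not reach the per-protocol definition. Intent, detection and a possible violation do not take a dose-compliant participant out of a set defined only by capsule count and acute treatment. Nor does it explain why tobramycin has an explicit hold line at Visit 1 and the randomized drug has none.

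**Conclusion.** The point holds as a minor one. The per-protocol rule, as written in three places, keeps exposed placebo participants, so that sensitivity analysis cannot address the most direct form of contamination. The missing entry in 7.3 and the missing Visit 1 line are gaps in explicitness: other text can be read to the same end, and most sites would probably infer the switch.

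The size is unknown. The loss in Step 3 is small unless continuation is common or the true effect is near the smallest that the sample size was built to detect. The protocol regards SD 13 as conservative and cites recent values of 8 to 11. A reader might conclude that the trial is underpowered. The documents do not support that: the stated power figures reproduce and assume no contamination, and nothing in the documents suggests a particular rate. The calculation also assumes full loss of effect in each continuer, apart from the half-loss variant.

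**What to change.** 1. **Per-protocol definition (15.1, SAP 2.4, SAP A.3).** Add: *no non-study chronic azithromycin or other chronic macrolide between Visit 1 and Visit 3*. Tabulate such use by arm from the concomitant-medication record, which already holds drug, frequency and dates (9.1.1).
2. **Section 7.3 and the synopsis.** List non-study chronic azithromycin and other chronic macrolides as prohibited, with acute courses left to 7.2. For Visits 1 to 3 this protects the contrast. For Visits 3 to 5, when every extension participant takes azithromycin, it serves only to avoid double dosing. Continued use then falls plainly under section 13.
3. **Section 10.1 and Appendix 1.** Beside the tobramycin hold, add a Visit 1 line telling participants in both arms to stop their home azithromycin supply.

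Leave 8.6.2 as it is. Limiting it to acute macrolides would narrow an existing safeguard.

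The cost is one clause in three places, one table row, one prohibited-medication entry in two places and one visit line in two places. No procedure, visit, data item or participant is added, and the m-ITT primary analysis and sample size stay as planned.

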## 7.2 Conditionally Allowed Medications and Treatments

Acute treatment with drugs categorized as known to prolong QT interval is allowed according to the following:

- For drugs commonly used to treat CF patients (e.g. ciprofloxacin, levofloxacin, moxifloxacin, fluconazole, propofol, sevoflurane, ondansetron), study drug (azithromycin or placebo) or open-label azithromycin **does not** need to be stopped.
- For all other drugs categorized as known to prolong QT interval, acute use is allowed but study drug (azithromycin or placebo) or open-label azithromycin **must** be temporarily stopped during use of these medications. After acute treatment is completed, subjects should re-start study drug or open-label azithromycin on the next scheduled treatment day.
- Ongoing chronic treatment (>30 days prior to Visit 1) with antidepressant medications citalopram and escitalopram is allowed without affecting study participation if:
  - The subject has been using both chronic oral azithromycin AND citalopram (or escitalopram) consistently for greater than 30 days at Visit 1 AND
  - The Visit 1 ECG demonstrates QTc within the normal limits as defined by the protocol

Drugs known to prolong QT interval are described as follows: “Substantial evidence supports the conclusion that these drugs prolong the QT interval AND are clearly associated with a risk of torsades de pointes (TdP), even when taken as directed in official labeling”, and listed on the CredibleMeds® Website ([Composite List of All QT Drugs](#) under the category “Known Risk of TdP”).

Acute use of macrolide antibiotics may be required for certain infections and is allowed but also requires temporarily stopping the study drug or open-label azithromycin. The study drug or open-label azithromycin should be restarted on the next scheduled day following completion of the prescribed macrolide antibiotic.

Treatment for pulmonary exacerbations as required for acute care is allowed except for treatments noted in the prohibited medications section below. Physicians are encouraged to prescribe acute antibiotic therapy and initiate or increase the dose of acute systemic corticosteroids (defined as less than 10 days) only in the presence of increased symptoms suggesting a pulmonary exacerbation.

